later without further practice (Retest 2). Each block consists of 50 key presses (ideally 10 sequences) and is followed by a rest block of 15-20 seconds without finger tapping. A two-minute rest period will be implemented after 14 blocks to further minimize the effects of fatigue on the last 4 blocks that are used to calculate the primary outcome. Performance on the MSL will be assessed using the 'Performance Index (PI)' [$PI = \exp^{-(\text{seqDur}(x))} * \exp^{-(\text{Errors}(x)/12)} * 100$], whereby (x) represents the blocks of the trials (King et al. 2017b). Given that both speed and accuracy determine the PI, these measures will be explored. During the single-task condition, participants view a fixation cross in the middle of the screen with the sequence presented above.

The primary outcome for experiment 1 will be the offline consolidation, measured as the change in PI between the first 4 blocks at Retest 1 immediately after the nap or wake intervention and the last 4 blocks of Learning immediately prior to the intervention. The primary outcome for experiment 1 will be analyzed with a repeated measures analysis of variance with the following factors and conditions: 4 blocks * 2 sessions (end of learning/begin of retest 1) * 2 groups (nap/wake) * 2 populations (pwPD/controls). Linear mixed models will be considered depending on the presence of missing values and interactions with covariates (age, gender, disease severity and levodopa equivalence dose) will be analyzed.

Experiment 2: The design of experiment 2 is similar to experiment 1, except that participants will learn two motor sequences that are visually and auditory cued by means of a serial reaction time task (SRT). After learning both sequences, participants will nap for 2 hours, but this time while the melody of one of the two sequences will be replayed using auditory TMR. Performance on both sequences will be re-assessed immediately after the intervention (Retest 1), and again at 24h retention (Retest 2) without cues.

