The primary outcome for experiment 2 is the 'offline consolidation' defined as the change in PI between the first 4 blocks at retest immediately after the nap and the last 4 blocks at learning prior to the intervention, which will be compared between the sequence that was replayed during the nap (replay) and the sequence that was not replayed (no-replay). The primary outcome for experiment 2 will be analyzed with a repeated measures analysis of variance with the following factors and conditions: 4 blocks * 2 sessions (end of learning/begin of retest 1) * 2 sequences (replay/no-replay) * 2 groups (pwPD/controls). Linear mixed models will be considered depending on the presence of missing values and interactions with covariates (age, gender, disease severity and levodopa equivalence dose) will be analyzed.

Secondary outcomes

All other comparisons for experiments 1 and 2 are considered secondary in importance. The PI is used as the main dependent variable of interest for all secondary outcomes listed below, which will be compared across the two intervention groups (Nap/Wake) and two study populations (pwPD/Controls). An MSL with consecutive dual task condition is performed for an additional 4 blocks at learning, immediately after the intervention (Retest 1) and again after

24hrs of retention (Retest 2). The following comparisons will be analyzed for both experiments.

Single task performance (PI):

1. Retention, measured as the change in PI between the first 4 blocks at Retest 2 compared to the last 4 blocks at Retest 1.
2. Learning slope over 14 blocks during learning, prior to the intervention.
3. Learning slope over 14 blocks after the 24hr retention period (Retest 2)
4. End of learning performance assessed over the last 4 blocks during learning prior to the intervention (Learning)
5. Post-extensive practice performance assessed over the last 4 blocks immediately after the intervention (Retest 1)

Dual tasking performance (PI):

1. Offline consolidation measured as the change in PI between the 4 blocks of dual tasking at Retest 1 immediately after the intervention compared to the 4 blocks of dual tasking during learning for experiment 1, and differences on PI between sequences A and B during the 4 blocks at Retest 1 for experiment 2.

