2. Retention, measured as the change in PI between the 4 blocks of dual tasking at Retest 2 compared to the 4 blocks of dual tasking at Retest 1 for experiment 1, and differences on PI between sequences A and B during the 4 blocks at Retest 2 for experiment 2.
3. Learning performance over the 4 blocks of dual tasking during learning prior to the intervention for experiment 1 only.
4. Learning performance over the 4 blocks of dual tasking immediately after the intervention (Retest 1) for both experiments.
5. Learning performance over the 4 blocks of dual tasking after the 24hr retention period (Retest 2) for both experiments.

Dual task cost (Δ PI), i.e. the difference in PI between 4 blocks of dual tasking and 4 blocks of single tasking.

1. Offline consolidation measured as the change in Δ PI between Retest 1 immediately after the intervention (4 blocks of dual tasking versus last 4 blocks of single tasking) and the Δ PI during learning (4 blocks of dual tasking versus the first 4 blocks of single tasking) for experiment 1, and difference in Δ PI between sequences A and B (4 blocks of dual tasking versus last 4 blocks of single tasking) at Retest 1 for experiment 2.
2. Retention, measured as the change in Δ PI between Retest 2 (4 blocks of dual tasking and last 4 blocks of single tasking) and Retest 1 (4 blocks of dual tasking and last 4 blocks of single tasking) for experiment 1, and difference in Δ PI between sequences A and B (4 blocks of dual tasking versus last 4 blocks of single tasking) at Retest 2 for experiment 2.
3. Learning performance assessed as the Δ PI of the 4 blocks of dual tasking and first 4 blocks of single tasking during learning for experiment 1 only.
4. Post extensive practice assessed as the Δ PI of the 4 blocks of dual tasking and last 4 blocks of single tasking immediately after the intervention (Retest 1) for both experiments.

5. Post extensive practice assessed as the Δ PI of the 4 blocks of dual tasking and last 4 blocks of single tasking after the 24hours retention period (Retest 2) for both experiments.

Control comparisons (PI): For experiment 2, four additional comparisons will be analyzed to ensure that participants could learn both sequences equally well. The two sequences can be labeled as either (sequence A / sequence B), irrespective of which sequence was replayed during the nap period, or as (replay / no-replay) respective of the sequence that was replayed during the nap period.

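### Experiment 1 dual-task cost, item 1: unmatched single-task references make the score not an offline measure, and it absorbs the Learning gain if dual tasking follows training

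*SAP*

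**What the plan says.** All places are in the SAP.

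- **Secondary outcomes, Dual task cost, definition.** Δ PI is given as "i.e. the difference in PI between 4 blocks of dual tasking and 4 blocks of single tasking". No sign is fixed.
- **Dual task cost, item 1, Experiment 1 (labelled offline consolidation).** One term is "Retest 1 immediately after the intervention (4 blocks of dual tasking versus last 4 blocks of single tasking"). It is set against a Learning term, which reads "Δ PI during learning (4 blocks of dual tasking versus the first 4 blocks of single tasking) for experiment 1".
- **Item 2 (retention).** The last 4 single-task blocks are the reference at both Retest 2 and Retest 1.
- **Item 3.** The same early reference is used at Learning: "Δ PI of the 4 blocks of dual tasking and first 4 blocks of single tasking during learning for experiment 1 only".
- **Item 4.** The Retest 1 term of item 1 appears again under another name, quoted here in part: "Post extensive practice assessed as the Δ PI of the 4 blocks of dual tasking and last 4 blocks of single tasking immediately after".
- **Primary outcome, Experiment 1.** Offline consolidation is a change in PI, and the blocks compared are these: "first 4 blocks at Retest 1 immediately after the nap or wake intervention and the last 4 blocks of Learning immediately prior to the intervention".
- **Secondary outcomes, opening paragraph.** On the dual-task blocks: "An MSL with consecutive dual task condition is performed for an additional 4 blocks at learning", and likewise at both retests. On the contrasts: PI is the dependent variable for the secondary outcomes, "which will be compared across the two intervention groups (Nap/Wake) and two study populations (pwPD/Controls").

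**The concern.** Item 1 uses the opposite ends of the two sessions from those that the primary outcome uses for offline consolidation. Learning has 18 single-task blocks, so 10 blocks of practice lie between the first 4 and the last 4. The SAP expects improvement over them, since the learning slope is itself a secondary outcome.

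A score whose single-task part runs from the start of Learning to the end of Retest 1 cannot isolate what happened over the nap or wake period. If dual tasking is done after training, it is also compared at Learning with performance from before training. A difference between patients and controls in how much they learned before the intervention could then be reported as a difference in consolidation, which is the question the study asks.

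**Working it through.** There is no SAP figure to reproduce, because the point concerns a definition. All numerical levels, gains and costs below are assumptions; the SAP gives none.

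**1. What the single-task part contains.** Write the single-task PI levels as

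- first 4 at Learning: a
- last 4 at Learning: a + g (g = Learning gain)
- first 4 at Retest 1: a + g + o (o = offline change)
- last 4 at Retest 1: a + g + o + r (r = Retest 1 practice gain)

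The single-task part of item 1 is (a + g + o + r) − a = g + o + r. The primary outcome's single-task contrast is (a + g + o) − (a + g) = o.

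**2. The score by task order.** Take Δ PI as dual minus single (the other convention flips every sign). Let dual-task PI be the adjacent single-task level minus a constant cost c, so the true change in cost is 0. Item 1 = (dual at Retest 1 − last 4 at Retest 1) − (dual at Learning − first 4 at Learning). With g = 8, r = 2, c = 3:

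| Dual task at Learning / Retest 1 | Item 1 as written | Last 4 at both sessions | Adjacent blocks |
|---|---|---|---|
| after / after | −g = −8 | 0 | 0 |
| after / before | −g − r = −10 | −2 | 0 |
| before / before | −r = −2 | +6 | 0 |
| before / after | 0 | +8 | 0 |

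Setting o = 5 instead of 0 changes none of the as-written values. The 0 in the last row does not make that order offline. If training alone lowers the cost from 5 to 3, item 1 there is (−3) − (−5) = +2 with no offline change.

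**3. The identity behind the first row.** By arithmetic, item 1 as written = (change with last-4 references at both sessions) − (last 4 minus first 4 single-task PI at Learning). When dual tasking follows training, the last 4 are the adjacent blocks, so the subtracted term is pure bias.

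**4. Size of the Learning gain.** The SAP's formula is PI = 100 · exp(−duration) · exp(−errors/12). With 1 error per block:

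| Assumed duration, first to last 4 (s) | PI, first to last 4 | Gain |
|---|---|---|
| 3.0 to 2.5 | 4.58 to 7.55 | 2.97 |
| 2.0 to 1.6 | 12.45 to 18.58 | 6.12 (unrounded PI) |
| 2.5 to 1.5 | 7.55 to 20.53 | 12.98 |
| 3.0 to 1.5 | 4.58 to 20.53 | 15.95 |

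The bias in item 1, if dual tasking comes last at both sessions, is therefore roughly 3 to 16 PI points.

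**5. Item 3.** With no errors, Learning from 2.0 to 1.4 s and a dual-task cost of 0.2 s, single-task PI goes from 13.53 to 24.66, and dual-task PI after training is 100 · exp(−1.6) = 20.19. As written, item 3 is 20.19 − 13.53 = +6.66, an apparent dual-task benefit. Against the last 4 it is 20.19 − 24.66 = −4.47, the real cost.

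**6. Patients versus controls, dual tasking last, no offline change.** PI is exponential in duration, so equal gains in seconds give unequal gains in PI. For controls from 2.0 to 1.4 s, item 1 is −11.13. For patients from 3.0 to 2.4 s, it is −(9.07 − 4.98) = −4.09. Control minus patient is about −7.0 as written and 0 with last-4 references.

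**7. Nap versus wake.** The subtracted gain arises before the intervention. If the groups are comparable at Learning, it has the same expectation in both and cancels from their difference.

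**8. Precision.** The matched change and the Learning gain share the last-4 Learning mean. With equal independent errors of variance s² on each mean, the matched change has variance 4s², the gain 2s², and their covariance is 1s². The as-written variance is 4 + 2 − 2·1 = 4 (times s²), the same as the matched one.

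**The case against.** The strongest reply has four parts.

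- **The early reference looks deliberate.** Items 1 and 3 both use it, and item 1 is simply item 4 minus item 3. If dual tasking comes first at Learning, the first 4 blocks are the right neighbours and item 3 is sound. This stands, and imposing last-4 references regardless of order would then do harm (+6 or +8 in the table where the true change is 0).
- **Task order is not in the SAP.** The wording about additional, consecutive blocks leans towards dual tasking after training. The primary outcome's placing of the last 4 Learning blocks directly before the intervention leans the other way. Order may also be set in the protocol, which is not at hand. This stands, so the bias by the Learning gain is conditional.
- **The label is partly terminology.** The plain dual-task outcome is also called offline consolidation, with only one set of 4 blocks per session. True, but there the blocks at least correspond between sessions. In item 1 the reference blocks do not.
- **The intervention contrast survives.** This also stands. A reader might infer that the nap-versus-wake comparison of item 1 is invalid, or that it loses a calculable amount of power. The document supports neither. The Learning gain cancels in expectation if groups are comparable at Learning. Any loss of precision depends on how much the gain truly varies between people and may be nil, so no power figure is claimed.

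**Conclusion.** The mismatch is certain from the text. As written, item 1 for Experiment 1 is not an offline measure in any task order, and it conflicts with the SAP's own definition in the primary outcome.

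The bias is conditional:

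- **Dual tasking after training.** The within-group change is shifted by the whole Learning gain, roughly 3 to 16 PI points on assumed durations. The patient-versus-control contrast is shifted by the difference in gains between the populations. Item 3 can show a benefit where there is a cost.
- **Dual tasking first at Learning.** Item 3 is sound and the Learning reference is right, but item 1 still spans online practice. If dual tasking also comes first at Retest 1, the last-4 reference there brings in the Retest 1 practice gain.

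It would go too far to say that the SAP puts dual tasking last, or that the study's main conclusions are at risk. Only secondary outcomes of Experiment 1 are touched; the primary outcome and the sample size are unaffected. Severity is minor to should-fix.

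**What to change.** State, for each session, where the dual-task blocks fall, and state the sign of Δ PI. Then reference Δ PI at each session to the single-task blocks adjacent to the dual-task blocks:

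- If dual tasking follows training at Learning, use the last 4 single-task blocks there in items 1 and 3, and keep the first-4 comparison as descriptive.
- If it comes first at Learning, keep the first 4 there. If it also comes first at Retest 1, use the first 4 at that session too.

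Describe item 1 as a between-session change in dual-task cost. Keep the offline consolidation label only if the blocks used are the end of Learning and the start of Retest 1.

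The cost is SAP wording only: every single-task block needed is already planned and no new data are required.

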1. End of learning performance on sequence A and B will be assessed as the difference in PI between the last 4 blocks of sequence A and the last 4 blocks of sequence B during learning prior to the intervention.
2. Learning slopes of sequence A and B will be assessed as the difference in PI between the first 14 blocks of sequence A and the first 14 blocks of sequence B during learning prior to the intervention.
3. End of learning performance on the replay and no-replay sequences will be assessed as the difference in PI between the last 4 blocks of the TMR sequence and the last 4 blocks of the control sequence during learning prior to the intervention.
4. Learning slopes of the replay and no-replay sequences will be assessed as the difference in PI between the first 14 blocks of sequence A and the first 14 blocks of sequence B during learning prior to the intervention.

Tertiary outcomes

Experiment 1 - Motor Execution Test (MET)

Participants perform a self-initiated MET by tapping a simple 4-element (i.e. 4-3-2-1) finger sequence presented on screen as rapidly and accurately as possible with their non-dominant hand for 4 blocks during learning and again for 4 blocks at each retest assessment. Each block consists of 52 key presses (ideally 13 sequences) and is followed by a rest block of 15-20 seconds without finger tapping. Performance on the MET will be compared between Retest 1 and learning and between Retest 2 and Retest 1.

Experiment 2 - Random Serial Reaction Time task (random SRT)

Participants will perform random sequences that are visually cued by means of a SRT for 4 blocks at learning and again at each retest assessment. Each block consists of 50 key presses and is followed by a rest block of 15-20 seconds without finger tapping. Performance on the random SRT will be compared between Retest 1 and learning and between Retest 2 and Retest 1.

Psychomotor Vigilance Test (PVT):

The MSL (Experiment 1) and SRT (Experiment 2) tests will be preceded by a 10-minute PVT as an objective measure of the participants' vigilance prior to testing. The PVT will be presented on a laptop and subjects will be instructed to press a button as quickly as possible each time a visual stimulus is presented in the middle of the screen. Changes in PVT performance (number of lapses in attention defined as response times \geq twice the median response time) will be

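### The Experiment 2 learning-slope control comparisons (items 2 and 4) are defined as a difference in PI, which read literally is a level contrast and cannot separate an offset from a difference in learning rate

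*SAP*

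**What the plan says.** The SAP, under 'Control comparisons (PI)', adds checks for Experiment 2: "four additional comparisons will be analyzed to ensure that participants could learn both sequences equally well". Two of the four concern learning slopes.

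- Item 2: "Learning slopes of sequence A and B will be assessed as the difference in PI between the first 14 blocks of sequence A", compared with the same blocks of sequence B.
- Item 4: "Learning slopes of the replay and no-replay sequences will be assessed as the difference in PI between the first 14 blocks of sequence A", again compared with sequence B.

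Items 1 and 3 concern end-of-learning performance and have the same form over a different window. Item 1 reads "End of learning performance on sequence A and B will be assessed as the difference in PI between the last 4 blocks of sequence A", compared with the same blocks of sequence B.

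Two other places bear on the reading. Under 'Secondary outcomes', single-task item 2 is "Learning slope over 14 blocks during learning, prior to the intervention", with no estimator; item 3 is the corresponding slope at Retest 2, also without one. Under 'Primary outcome', the Experiment 2 analysis is a repeated measures ANOVA with factors "4 blocks * 2 sessions (end of learning/begin of retest 1) * 2 sequences (replay/no-replay) * 2 groups (pwPD/controls"), so block is a named factor there. No such model is stated for the control comparisons.

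**The concern.** PI is a performance score for a block. A difference in PI between two sets of blocks is therefore a difference in level. A learning slope is the rate at which PI changes from block to block, and nothing in items 2 and 4 refers to change over blocks. The same formula serves for end performance in items 1 and 3 and for slope in items 2 and 4; only the window differs.

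The checks support the reading of the within-participant replay versus no-replay comparison, since their purpose is "to ensure that participants could learn both sequences equally well". If the slope check is run as worded, a sequence that is merely easier to tap, but learned at the same rate, appears to have a different slope. Conversely, a real difference in rate may go unseen if it is offset by a difference in starting level. Either way, the result could not be reported as a statement about learning rate.

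**Working it through.** The SAP states no figure for these comparisons, so there is none to reproduce. The check compares the literal contrast with a slope contrast on straight-line curves.

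**Definitions.** Let d(b) be the mean PI difference between the two sequences at block b, for b = 1 to 14, with d(b) = m + s × (b − 7.5). Here m is the difference in 14-block mean and s the difference in slope.

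- Literal contrast: the average of d(b) over 14 blocks, which equals m. It does not contain s.
- Slope contrast: Σ(b − 7.5) d(b) / Σ(b − 7.5)², which equals s. It does not contain m. The denominator is 227.5.

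**Four patterns.** For unequal rates, s = 0.4 PI per block.

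- Parallel, 2.5 PI apart: m = 2.5, s = 0.
- Crossing mid-practice: the gap runs from −0.4 × 6.5 = −2.6 at block 1 to +2.6 at block 14, so m = 0.
- Crossing early: the gap runs from −1.3 to −1.3 + 13 × 0.4 = +3.9, so m = (−1.3 + 3.9)/2 = 1.3.
- Common start: the gap runs from 0 to 13 × 0.4 = 5.2, so m = 2.6. A common end gives the same size with the opposite sign.

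**Assumed variability** (none of it from the SAP): between-participant SD of the level difference 4 PI; of the slope difference 0.5 PI per block; block noise SD 3 PI per sequence, hence variance 18 for a difference.

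- SD of a participant's mean difference: √(16 + 18/14) = 4.16.
- SD of a participant's slope difference: √(0.25 + 18/227.5) = 0.574.

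**Sample size.** The 'Power calculation' section targets 20 pwPD and 20 controls, so n = 40; after 20% dropout, 40 × 0.8 = 32.

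- Standard errors at n = 40: 4.16/√40 = 0.657 and 0.574/√40 = 0.0907.
- Standard errors at n = 32: 4.16/√32 = 0.735 and 0.574/√32 = 0.101.

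**Rejection rates**, paired t-test, two-sided 5%, noncentral t with noncentrality m or s divided by its standard error (for example 2.5/0.657 = 3.80 and 0.4/0.0907 = 4.41):

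| Pattern | Literal, n = 40 | Slope, n = 40 | Literal, n = 32 | Slope, n = 32 |
|---|---|---|---|---|
| Parallel, 2.5 PI apart | 96% | 5% | 91% | 5% |
| Crossing mid-practice | 5% | 99% | 5% | 97% |
| Crossing early (−1.3 to +3.9) | 49% | 99% | 40% | 97% |
| Common start (or end) | 97% | 99% | 93% | 97% |

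**A second set of assumptions** (simulation, n = 20, block SD 5, level-difference SD 4, slope-difference SD 0.4) gives the same pattern, literal versus slope contrast:

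- Parallel curves 5 PI apart: about 100% versus 5%.
- Slopes 0.5 and 1.5 crossing mid-practice: about 5% versus 100%.
- Common start, slopes 1.0 and 1.5 (m = 0.5 × 6.5 = 3.25): 88% versus 94%.
- Common end, slopes 0.5 and 1.5: about 100% for both.

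The percentages depend on the assumed SDs and curves. That the literal contrast equals m and the slope contrast equals s does not.

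**The case against.** The strongest reply is that the text is loosely worded rather than wrong. The SAP also describes the primary outcome as a change in PI between two sets of blocks and then analyses it with block as a factor. Carried over, that style gives a 14-block by 2-sequence analysis whose interaction does test whether the curves differ, and the name of the comparison shows that slope was intended. This stands in part: a reader might infer that the SAP has deliberately fixed a comparison of means, and it does not go that far. But it states no such model for items 2 and 4. Even in that model, the term matching a difference in PI is the sequence main effect; the interaction would have to be named.

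A reader might also infer that the check is generally blind to unequal learning rates. It is not. Two new sequences may well start at similar levels, and then unequal rates shift the 14-block mean and are usually detected (97% above at n = 40). Sensitivity is lost only when the curves cross during practice, most of all near the middle.

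Nor do the documents show that items 2 and 4 repeat items 1 and 3. On the 18-block layout described for Experiment 1, to which Experiment 2 is said to be similar, the first 14 and last 4 blocks do not overlap.

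Finally, an offset during acquisition does bear on whether both sequences were learned equally well. Flagging it is useful; calling it a slope difference is the error.

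**Conclusion.** The point holds in a limited form. Items 2 and 4 carry the name of a slope, give no slope estimator, and are defined in words that literally yield a difference in PI level. Followed as written, they attribute any level offset to slope, can miss unequal rates when the curves cross, and cannot identify a rate difference when they do reject. The first of these needs no special curve shape: whenever there is a true offset, the literal contrast targets a non-zero value even if the slopes are equal.

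The size is illustrative only and rests on straight-line curves and assumed SDs.

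A reader might infer that the Experiment 2 primary result is compromised. The documents do not support that: the primary outcome is a change within each sequence from the end of learning, items 1 and 3 check that starting level directly, and the primary model does not use items 2 and 4. The effect is confined to supporting control checks. It should still be corrected, because the choice between a level and a slope test should not be left until the data are seen.

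**What to change.** Redefine items 2 and 4 as the difference in learning rate between the sequences over learning blocks 1 to 14. Either of two forms will do: the sequence-by-block linear-trend interaction, or a paired test of least-squares slopes fitted per participant and sequence. State which one, and use the same slope definition for single-task secondary outcomes 2 and 3, which currently have none. Keep items 1 and 3 as the level checks.

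While editing, note a separate slip: item 4 is headed replay/no-replay but written in A/B labels, so as it stands it repeats item 2. Correcting the labels alone would leave the contrast a level.

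The cost is about two sentences in the control comparisons, plus a matching definition for the two secondary outcomes. It needs no new data and does not change the sample size or the primary analysis.

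### Control comparison 4 is headed as a replay/no-replay slope check but is defined as sequence A versus B, so it repeats comparison 2 and the slope check by replay status is missing

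*SAP*

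**What the plan says.** The SAP, under Control comparisons (PI), says that for Experiment 2 "four additional comparisons will be analyzed to ensure that participants could learn both sequences equally well". It sets up two labelings. In one, "The two sequences can be labeled as either (sequence A / sequence B), irrespective of which sequence was replayed during the nap period". In the other, the labels replay and no-replay follow from which sequence was played back during the nap.

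The four items are then:

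- Item 1: end-of-learning level, last 4 blocks, A versus B.
- Item 2: "Learning slopes of sequence A and B will be assessed as the difference in PI between the first 14 blocks of sequence A", set against the same blocks of sequence B.
- Item 3: end-of-learning level by replay status, as the "difference in PI between the last 4 blocks of the TMR sequence and the last 4 blocks of the control sequence".
- Item 4: "Learning slopes of the replay and no-replay sequences will be assessed as the difference in PI between the first 14 blocks of sequence A", again set against the same blocks of sequence B.

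Under Primary outcome, the Experiment 2 analysis has a two-level sequence factor coded replay/no-replay and uses the last 4 blocks of learning and the first 4 blocks of Retest 1.

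**The concern.** Item 4 announces a comparison by replay status and then defines one by A/B label. An analyst who follows the definition reports item 2's result a second time under a replay/no-replay heading. A reader would take that as evidence that the two sequences were learned at the same rate whichever was later replayed, although this had not been tested. An analyst who follows the heading departs from the written definition. Either way, report and plan disagree.

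Replay status is the coding that matters most for this check, because the Experiment 2 effect is the replay versus no-replay contrast. The A/B comparison answers a different question: whether one sequence is harder than the other.

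**Working it through.** The SAP gives no figure to reproduce here, so the main check is a comparison of text.

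**Step 1: the layout.**

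| | By A/B label | By replay status |
|---|---|---|
| End-of-learning level (last 4 blocks) | Item 1: A vs B | Item 3: TMR vs control sequence |
| Learning slope (first 14 blocks) | Item 2: A vs B | Item 4: heading says replay vs no-replay; definition says A vs B |

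After their headings, items 2 and 4 are identical. Four comparisons are promised and three distinct contrasts are defined: item 1, item 2 (the same as item 4) and item 3. The cell for slope by replay status is empty.

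**Step 2: can A/B stand for replay/no-replay?** No. The SAP defines the labels as "sequence A / sequence B), irrespective of which sequence was replayed during the nap period". If A were always the replayed sequence, items 1 and 3 would also coincide and the second labeling would have no use.

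**Step 3: does another analysis fill the empty cell?** The general single-task outcome is "Learning slope over 14 blocks during learning, prior to the intervention". It is to be compared across nap/wake group and population, and no sequence factor is named. The primary Experiment 2 model uses only the last 4 learning blocks and the first 4 Retest 1 blocks, so it does not cover the slope over the first 14 blocks.

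**Step 4: how much could the A/B contrast say about replay status?** This is an illustration. The share p of participants who have A replayed is not in the SAP.

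Let d be a participant's replay minus no-replay difference before the nap, with mean δ. Let s = +1 if A was replayed and −1 if B was. Then A − B = s × d. With no true difficulty difference between A and B:

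- mean of (A − B) = p × δ + (1 − p) × (−δ) = (2p − 1) × δ
- correlation between the two estimated mean differences, when the true δ is zero = 2p − 1

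A true A/B difficulty difference would simply be added to the A − B mean.

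The last column comes from simulation with n = 40 (the Experiment 2 target of 20 + 20), normal d, true δ zero and 100,000 runs. It shows how often the A/B coding also flags a chance imbalance that is significant at 5% in the replay coding.

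| p | 2p − 1 | Also flagged by A/B coding |
|---|---|---|
| 0.50 | 0.00 | about 4% |
| 0.65 | 0.30 | about 8% |
| 0.75 | 0.50 | about 16% |
| 1.00 | 1.00 | 100% |

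If the replayed sequence were assigned by simple 1:1 randomisation (also an assumption):

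- n = 40: the count with A replayed falls in 14 to 26 with probability 0.96. The largest 2p − 1 is 2 × 26/40 − 1 = 0.30, so shared variance is at most 0.30² = 9%.
- n = 32 (2 × 16, the minimum before the dropout allowance): the range 11 to 21 has probability 0.95. The largest 2p − 1 is 2 × 21/32 − 1 = 0.31, so shared variance is at most about 10%. The wider range 10 to 22 has probability 0.98, with a largest 2p − 1 of 0.375 and shared variance of at most 14%.

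Unless nearly everyone had the same sequence replayed, the A/B slope comparison is a poor substitute for the one by replay status.

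**The case against.** The best reply is that this is a recoverable copy error. The heading of item 4 is clear, item 3 shows the pattern, and only one cell of the layout is left for item 4, so a sensible analyst would work out what was meant. Little also hangs on it. The primary analysis carries the replay/no-replay factor and measures change from end of learning, item 3 checks that baseline by replay status, and the first 14 blocks do not enter the primary outcome. The comparison precedes the nap, so replay cannot have caused any difference it shows. Finally, the stated purpose concerns the two sequences as such, which items 1 and 2 address.

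Most of this stands as a limit on the consequence. It does not remove the error. The definition is the operative instruction, and it conflicts with its own heading. Equal end levels do not show equal learning rates, and the SAP itself lists slopes separately and names replay status for them.

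Two further cautions are fair. The figures in step 4 rest on assumptions about p, normality and equal difficulty, and the case does not need them. The general secondary-outcome sentence about nap and wake groups fits Experiment 2 poorly, since all its participants nap. Its silence on sequence is therefore weak evidence of intent, although it remains true that no stated analysis covers the missing contrast.

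**Conclusion.** The point holds. As written, item 4 is item 2 under another heading: two of the four control comparisons are the same contrast, and no learning-slope comparison by replay status is defined anywhere in the SAP. This follows from the text alone and needs no assumption. How little the A/B contrast could reveal about replay status depends on the unstated split p; with a balanced split it reveals nothing about a mean imbalance.

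The consequence is limited to a supplementary pre-nap check. The primary Experiment 2 estimate is unaffected. The correction should be made because the present wording could put a balance claim in the report that was never tested.

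**What to change.** Redefine item 4 as the difference between the first 14 learning blocks of the replayed (TMR) sequence and the first 14 learning blocks of the non-replayed (control) sequence, in line with item 3. Leave item 2 as the A/B comparison.

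While the text is open, it would help to say in items 2 and 4 how a slope is compared, for example as the block-by-sequence interaction over blocks 1 to 14 or as the difference between each participant's two fitted slopes. A difference in PI over 14 blocks can also be read as a difference in mean level. This is a clarification, and the finding does not rest on it.

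The cost is SAP wording only, with no change to data collection, sample size or the primary analysis.
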